### **13.4. Reporting Serious Adverse Events**

All SAEs (related and unrelated) will be recorded from signing of consent form through the last study visit. Any SAEs considered possibly, probably, or definitely related to the investigational product and discovered by the Investigator at any time after the study should be reported. All SAEs must be reported to AveXis via Syneos Health within 24 hours of the first awareness of the event. The Investigator must complete, sign and date the SAE pages, verify the accuracy of the information recorded on the SAE pages with the corresponding source documents, and send a copy by fax or email to Syneos Health.

Additional follow-up information, if required or available, should all be faxed or emailed to Syneos Health within 24 hours of receipt and this should be completed on a follow-up SAE form, and placed with the original SAE information and kept with the appropriate section of the eCRF and/or study file.

AveXis is responsible for notifying the relevant regulatory authorities of certain events. It is the Principal Investigator's responsibility to notify the IRB/IEC of all SAEs that occur at his/her site, as per IRB/IEC reporting guidelines. Investigators will also be notified of all unexpected, serious, drug-related events (7/15 Day Safety Reports) that occur during the clinical trial. Each site is responsible for notifying its IRB/IEC of these additional SAEs.

### **13.5. Expedited Safety Reporting to Regulatory Authorities**

All unexpected, serious, drug-related events which are fatal or life-threatening will be reported to relevant regulatory authorities in an expeditious manner. All other unexpected, serious, drug-related events will be reported to relevant regulatory authorities within 15 days.

## 14. STATISTICS

### 14.1. Statistical Methods

A Statistical Analysis Plan (SAP) will be developed that describes in detail the statistical methods to be used for analysis of this study and will be finalized prior to study enrollment.

### 14.2. General

Binary endpoints (e.g., standing without support) will be compared between AVXS-101 and natural history control groups using a 2-sided Fisher's Exact Test at level of 0.05. A 95% exact unconditional confidence interval for the true population difference in response rates will be computed.

Results involving continuous endpoints (e.g., change in HFMSE) will be compared between AVXS-101 and natural history control groups at 2-sided significance level  $\alpha=0.05$  using analysis of variance (ANOVA), or non-parametric Wilcoxon Rank Sum test, as appropriate.

All statistical tests will be conducted at a significance level of 0.05.

### 14.3. Analysis Populations

#### 14.3.1. Full Analysis Set

The full analysis set consists of all patients who receive the AVXS-101 injection.

#### 14.3.2. Intent-to-Treat

The Intent-to-Treat (ITT) Set will include all enrolled patients who receive AVXS-101 IT injection treatment. Patients will be analyzed according to the assigned dose. All efficacy analyses will be conducted using the ITT Set as the primary population, unless specified otherwise.

#### 14.3.3. Enrolled Set

The Enrolled Set will include all patients enrolled (i.e., completed the informed consent process). Unless specified otherwise, this set will be used for patient listings and for summaries of patient disposition.

#### 14.3.4. Efficacy Completers Analysis Set

The Efficacy Completers Analysis Set consists of all treated patients who complete 12 months following AVXS-101 dose procedure.

#### 14.3.5. Safety Analysis Set

The safety analysis set consists of all patients who receive the AVXS-101 injection.

### 14.4. Sample Size Calculation

This is a Phase 1 trial with determination of optimal dose as primary objective, using both safety and efficacy measures on motor function assessments. Secondary outcomes include the

achievement of milestones and change from baseline on HFMSE and fine and gross motor portions of the Bayley Scales of Infant and Toddler Development.

This study is designed to assess the impact of AVXS-101 on non-ambulatory young children with SMA who have 3 copies of *SMN2*, with efficacy outcomes specifically assessing improvement in motor function from that expected in the natural history of non-ambulatory children with SMA. Data will be compared with patient-level data drawn from a widely (peer-reviewed) published natural history dataset collected by the Pediatric Neuromuscular Clinical Research (PNCR) network.

Although patients with SMA Type 2 and 3 are easily differentiated in a retrospective manner by best clinical function, given the clinical overlap between the two phenotypes it is difficult at the time of diagnosis to predict the ultimate clinical course for a given individual patient at the time of initial diagnosis. From the published literature from a large natural history study (Kaufman 2012), we believe that a significant majority of the patients eligible for this study will, in fact, have SMA Type 2. However, it is also expected based upon this literature that a small percentage of children eligible for this study (3 copies of *SMN2*, age of symptom onset less than 12 months, sitting but not standing or walking independently) will, in fact, be children who would ultimately walk independently as part of the normal course of their disease (and therefore would be ultimately re-classified as SMA Type 3). The study design, statistical considerations, and study size are based upon this presumption.

Patients will be stratified into 2 groups based upon age at dosing. Between Dose A and Dose B 15 patients will be enrolled aged  $\geq 6$  months and  $< 24$  months at dosing, and 12 patients will be enrolled who are aged 24 months to  $< 60$  months at the time of dosing. Up to an additional 24 patients may be enrolled and receive a higher dose (Dose C) if deemed appropriate and necessary by AveXis and approved by the DSMB/DMC (see [Section 15](#)).

The primary efficacy endpoint for the group of patients  $\geq 6$  months and  $< 24$  months of age at time of dosing will be the proportion of treated patients who achieve the ability to stand without support up to the 12-month study visit. Twelve children aged  $\geq 6$  months and  $< 24$  months will be enrolled who receive Dose B. The proportion of patients developing the ability to stand without support will be compared with a cohort of eligibility-matched patients from the PNCR natural history study of SMA. Based upon a review of eligibility-matched patients from the PNCR, 14% of patients who meet the study criteria for patients  $\geq 6$  months and  $< 24$  months of age achieved the ability to stand without support, and 10% achieved the ability to walk without assistance. We expect 85% of treated patients  $\geq 6$  months and  $< 24$  months of age to achieve the ability to stand alone and 60% to achieve the ability to walk without support. With this efficacy a sample size of 12 patients would provide power of  $> 90\%$  to detect a significant difference compared with the matched control cohort with  $\alpha = 0.05$  using a two-sample 2-sided superiority Fisher exact test.

The primary efficacy endpoint will be the change in HFMSE in treated patients between 24 months and  $< 60$  months of age at time of dosing. Twelve children aged  $\geq 24$  months and  $< 60$  months will be enrolled. Change in HFMSE score at 12 months will be compared with a cohort of eligibility-matched patients from the PNCR natural history study of SMA. Based upon a review of eligibility-matched patients from the PNCR, a mean change of -1.33 points (standard deviation = 4.32 points) is seen at 12 months from baseline among patients aged 2-5 years at first evaluation with 3 copies of *SMN2* in the PNCR dataset. We expect to observe a mean increase

of 8 points from baseline on the HFMSE with equivalent variance. Based upon these assumptions, 12 patients between 24 and <60 months at enrollment will have >90% power to detect a significant difference with  $\alpha = 0.05$  when compared to patient-level data available from the PNCR dataset using two-sample ANOVA.

## **14.5. Demographic and Other Baseline Characteristics**

Continuous demographic and other baseline characteristics (age, months since symptom onset, etc.) will be summarized by dosing cohort using n, mean, SD, median, minimum, and maximum. Qualitative characteristics (such as gender and race) will be summarized by counts and percentages.

## **14.6. Efficacy Analysis**

### **14.6.1. Observation Period for Efficacy**

Efficacy comparisons will be made once all patients have either completed 15 months of follow-up or withdrawn prior to 15 months of follow-up. The primary analysis of efficacy data will be based on data collected through the 12-month time point; a supportive analysis of efficacy data will be based on data collected through the 15-month time point.

### **14.6.2. Primary Efficacy Endpoints**

Primary efficacy endpoints are assessed independently for each age group.

#### **14.6.2.1. Primary Efficacy Endpoint: patients $\geq 6$ months and $< 24$ months at time of dosing**

The primary efficacy endpoint is the proportion of patients  $\geq 6$  months and  $< 24$  months at time of dosing that achieve the ability to stand alone, without support for at least 3 seconds (Bayley Scales of Infant and Toddler Motor Development – Gross Motor subset item # 40) up to the 12-month study visit. A Responder for the primary endpoint of standing alone will be defined as per the Bayley Scales of Infant and Toddler Motor Development – Gross Motor subset item #40 – the child stands alone for at least 3 seconds after you release his or her hands.

The proportion of patients  $\geq 6$  months and  $< 24$  months of age at time of dosing achieving the ability to stand without support up to the 12-month study visit will be compared between AVXS-101 and natural history control groups using a two-sample 2-sided superiority Fisher exact test. A 95% exact conditional confidence interval for the difference in response rates will be computed.

The primary analyses will be based on the Full Analysis Set for patients  $\geq 6$  months and  $< 24$  months of age at the time of dosing.

A sensitivity analysis will be conducted by repeating each primary efficacy analysis on the Efficacy Completers Analysis Set for patients  $\geq 6$  months and  $< 24$  months of age at the time of dosing.

A supportive analysis will be conducted by repeating the analysis of the primary efficacy endpoint for patients  $\geq 6$  months and  $< 24$  months of age considering data through the 15-month visit.

#### **14.6.2.2. Primary Efficacy Endpoint: patients $\geq$ 24 months and $<$ 60 months at time of dosing**

The primary endpoint is the change from baseline in HFMSE for patients  $\geq$  24 months and  $<$  60 months of age at time dosing.

The primary efficacy analysis performed amongst patients aged between 24 months and  $<$  60 months of age at time of dosing will be the change from baseline in HFMSE at the 12-month study visit using a two-sample ANOVA at significance level of 0.05 (2-sided). A 95% confidence interval will be computed.

The primary analyses will be based on the Full Analysis Set for patients  $\geq$  24 months of age and  $<$  60 months of age at the time of dosing.

A sensitivity analysis will be conducted by repeating each primary efficacy analysis on the Efficacy Completers Analysis Set for patients  $\geq$  24 months of age and  $<$  60 months of age at the time of dosing.

A supportive analysis will be conducted by repeating the analysis of the primary efficacy endpoint for patients  $\geq$  24 months of age and  $<$  60 months of age considering data through the 15-month visit.

#### **14.6.3. Secondary Efficacy Endpoint**

The secondary endpoint for both patient strata (aged  $\geq$  6 months and  $<$  24 months at dosing, aged  $\geq$  24 and  $<$  60 months at dosing) will be the proportion achieving the ability to walk without assistance, defined as per the Bayley Scales of Infant and Toddler Motor Development – Gross Motor subset item # 43) up to the 12-month study visit. A Responder will be defined as a patient demonstrating achievement of the ability to walk without assistance at any post-procedure visit up to Month 12.

The proportion of patients  $\geq$  6 months and  $<$  24 months or  $\geq$  24 and  $<$  60 months at time of dosing who achieve the ability to walk without assistance will be compared separately between AVXS 101 and natural history control groups using two-sample Fisher's 2-sided exact test. A 95% exact confidence interval for the differences in response rates will be computed.

A supportive analysis will be conducted by repeating the analysis of the secondary efficacy endpoint considering data through the 15-month visit.

## 14.7. Safety Analysis

Safety will be assessed through monitoring AE reports and concomitant medication usage, and by conducting physical examinations, vital sign assessments, cardiovascular evaluations, and laboratory evaluations (chemistry, hematology, coagulation, immunology). Patients will be observed at the hospital for 48 hours post IT injection. Patients will return for follow-up visits in accordance with the SoA. Adverse events will be coded in accord with the most current version of the MedDRA coding dictionary.

### 14.7.1. Primary Safety Endpoints

#### 14.7.1.1. Safety and Tolerability of AVXS-101 IT Administration

The safety and tolerability of IT administration of AVXS-101 will be assessed through the incidence, severity, and relatedness of AEs up to the time of data lock.

The proportion of patients with any AE, any SAE; any AE related to study product, and any Grade III or higher AE will be summarized overall, and by Body System and Preferred Term. Incidence rates will also be reported by cohort.

#### 14.7.1.2. Determination of Optimal Dose

Up to 3 IT doses of AVXS-101 are examined in this dose escalation study. The DSMB/DMC's recommendation to escalate from Dose A to Dose B will be based on safety data as of the first quarterly DSMB/DMC meeting following enrollment of the third patient in Cohort 1. The recommendation to proceed to Cohort 2 signals the DSMB/DMC's evaluation that Dose A has acceptable safety.

Similarly, at the first quarterly DSMB/DMC meeting following enrollment of the third patient in Cohort 2, the DSMB/DMC will again evaluate safety data. The recommendation to expand Cohort 2 signals the DSMB/DMC's evaluation that the Dose B also has acceptable safety.

Based upon an ongoing assessment of safety and efficacy data from patients treated with Dose B, an option for testing of a third dose (Dose C), will be considered. If AveXis decides to proceed with testing of a third dose, a meeting of the DSMB/DMC will be convened to make recommendations regarding dose escalation. The DSMB/DMC's recommendation to escalate from Dose B to Dose C will be based on safety and efficacy. The recommendation to proceed to Cohort 3 signals the DSMB/DMC's evaluation that Dose B has acceptable safety.

### 14.7.2. Secondary Safety Endpoints

#### 14.7.2.1. Ventilatory Support

The number of hours per day of non-invasive ventilatory support will be captured continuously by the device. The n, mean, median, range of number of hours per day of non-invasive ventilatory support will be summarized by visit and cohort. At each visit and within cohort, the daily non-invasive ventilatory support use will be summarized for AVXS- 101.

## **15. DATA SAFETY MONITORING BOARD/DATA MONITORING COMMITTEE**

The DSMB/DMC is an independent multidisciplinary group consisting of clinicians and a biostatistician that, collectively, have experience in the management of patients with SMA Type 1 and other diseases, and in the conduct and monitoring of randomized clinical studies with interim analyses. The DSMB/DMC will be chartered to oversee the safety of patients during the conduct of the trial and will act in an advisory capacity to AveXis. A detailed description of the DSMB/DMC, its role in this trial, and the timing of the scheduled reviews will be described in a DSMB/DMC Charter.

The DSMB/DMC will routinely convene on a quarterly basis to review emerging safety data from the trial. All available safety data from all enrolled patients will be included in such reviews, which include, but are not limited to, screen failures, enrollment status, data from safety parameters, all SAEs, and other AEs. Following each meeting, the DSMB/DMC will make a recommendation as to whether or not the accumulated safety data warrants a suspension or discontinuation of the trial, a modification to the trial, or any additional comments or recommendations related to safety. The DSMB/DMC will prepare and provide minutes of their meetings to AveXis who will provide copies to the regulatory authorities as appropriate.

The DSMB/DMC will also convene on an ad hoc basis within approximately 48 hours should any patient experience an unanticipated CTCAE Grade 3 or higher AE/toxicity that is possibly, probably or definitely related to gene replacement therapy, and is associated with clinical symptoms and/or requires medical treatment. This includes any patient death, important clinical laboratory finding, or any complication attributed to administration of gene replacement therapy. In such instances, the DSMB/DMC will review the safety information and provide its recommendation. Based upon the DSMB/DMC's review, the DSMB/DMC can recommend continuing enrollment, halting enrollment or early termination of the trial for safety reasons.

### **15.1. DSMB/DMC Interim Safety Review**

Up to three interim safety reviews will be conducted by the DSMB/DMC. The first DSMB/DMC interim safety review will take place after three patients have been enrolled in Cohort 1. The consideration for this review is terminating the study for safety. In the absence of a termination recommendation, a recommendation to escalate enrollment to the higher dose is made.

The second DSMB/DMC interim safety review will take place after three patients have been enrolled in Cohort 2 (six total enrolled). The consideration for this review is terminating enrollment in Cohort 2 due to safety concerns. In the absence of a termination recommendation, a recommendation to expand the current Cohort 2 is made.

The third DSMB/DMC interim safety review may take place after three patients have been enrolled in Cohort 3. The consideration for this review is terminating enrollment in Cohort 3 due to safety concerns. In the absence of a termination recommendation, a recommendation to expand the current Cohort 3 is made.

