### 2.2. Timings of Analyses

#### 2.2.1. Primary Safety and Efficacy Analysis

Patients from Cohort 1 and Cohort 2 will be followed for a total of 12 months post-dose; patients from Cohort 3 will be followed for a total of 15 months post-dose. The primary analyses for efficacy will be assessed when all patients have completed 12 months of follow-up study visits following AVXS-101 administration, and the primary analyses for safety will be assessed when the last patient of Cohort 3 reaches 15 months post-dose (and database lock will take place after the last patient reaches 15 months post-dose).

On 18-November-2021, AveXis made the decision to terminate the study early. As a result, Cohort 3 did not enroll the full number of planned patients. Per the protocol, a total of 24 patients were planned to be enrolled into Cohort 3: 12 patients aged > 6 months and < 24 months and 12 patients aged  $\geq$  24 and < 60 months. When the decision was made to terminate the study early, a total of 4 patients aged > 6 months and < 24 months had been enrolled and treated in Cohort 3. Because of the early study termination, the majority of analyses pre-specified in the protocol to be conducted on patients in Cohort 3 are no longer applicable. Unless otherwise specified, the data collected for patients in Cohort 3 will be summarized using descriptive statistics and summarized in data listings.

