### 3.10. Study Flowchart and Schedule of Assessments

Figure 1: Study Design

 Four (4) week dosing between first three patients within each cohort to allow safety monitoring  
 Provided no dose related toxicities and DSMB determines acceptable to escalate/expand during quarterly meeting

Refer to Appendix 22.3 for the schedule of assessments.

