## **13. INTERIM SAFETY REVIEWS**

Up to three (3) safety reviews by the DSMB will be conducted. The DSMB will review the safety data extract from the database. The safety analysis specified in this SAP is not planned for the DSMB.

The first DSMB interim safety review will take place after three (3) participants in Cohort 1 have been dosed. The consideration for this review is terminating the study for safety. In the absence of a termination recommendation, a recommendation to escalate enrollment to the higher dose is made.

The second DSMB interim safety review will take place after three (3) participants in Cohort 2 have been dosed (6 total dosed). The consideration for this review is terminating enrollment in Cohort 2 due to safety concerns. In the absence of a termination recommendation, a recommendation to expand the current Cohort 2 is made.

The third DSMB interim safety review may take place after three (3) patients have been enrolled in Cohort 3. The consideration for this review is terminating enrollment in Cohort 3 due to safety concerns. In the absence of a termination recommendation, a recommendation to expand the current Cohort 3 is made.

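### Neither document requires the third child's Day 30 safety data before the first Dose B child is treated or before Cohort 3 is expanded, and the review trigger differs between protocol (enrolled) and SAP (dosed, for reviews 1 and 2)

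*Protocol*

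**What the plan says.** **Protocol.** Section 15.1 places review 1 "after three patients have been enrolled in Cohort 1" and uses the same word, enrolled, for reviews 2 and 3. It adds: "In the absence of a termination recommendation, a recommendation to escalate enrollment to the higher dose is made". Section 14.7.1.2 bases the step from Dose A to Dose B on "safety data as of the first quarterly DSMB/DMC meeting following enrollment of the third patient in Cohort 1". Section 14.3.3 (and SAP 5.2) defines the Enrolled Set by completed informed consent, not by dosing. Section 10.7 imposes a 4-week interval within Cohort 1 so that six safety time points (Days 1, 2, 7, 14, 21 and 30) can be reviewed before the next child is dosed. For Dose C it applies a four-week interval to the first three children only. In Cohort 2 the interval continues unless the sponsor lifts it after the DSMB's advice.

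**SAP.** Section 13 times review 1 for when three "participants in Cohort 1 have been dosed" and treats Cohort 2 likewise. For Cohort 3 it reverts to the protocol's word: "The third DSMB interim safety review may take place after three (3) patients have been enrolled in Cohort 3". The footnotes to Figure 1 (section 3.10) read "Four (4) week dosing between first three patients within each cohort to allow safety monitoring" and "Provided no dose related toxicities and DSMB determines acceptable to escalate/expand during quarterly meeting". Neither footnote sets a minimum follow-up on the third child. Section 2.2.1 records the early termination and says that four children "had been enrolled and treated in Cohort 3".

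**The concern.** Review 1 decides whether new children receive twice the dose. Review 3 decides whether up to 21 more children receive the highest dose. The product is given once and the dose cannot be adjusted afterwards (protocol 7.4).

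Within Cohort 1, the protocol wants Day 30 information on one child before another receives the *same* dose. It states no such condition on the third Dose A child before a new child receives *double* that dose. After the third Dose C child, no interval holds back the fourth. In a group of three, the third child is one third of the evidence at that dose level.

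The trigger word adds to this. Read literally, enrolled allows the review to take place before the third child has been dosed at all.

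**Working it through.** The plan states no figure on this point, so the check compares the texts and then does date arithmetic.

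**1. Passages side by side**

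| Step | Trigger in protocol | Trigger in SAP 13 | Spacing rule | Third child's Day 30 required? |
|---|---|---|---|---|
| Review 1, A to B | enrolled (15.1, 14.7.1.2) | dosed | 4 weeks, within Cohort 1 only (10.7) | No |
| Review 2, expand Cohort 2 | enrolled | dosed | 4 weeks, continuing unless the sponsor lifts it | Not stated; partly protected by the interval |
| Review 3, expand Cohort 3 | enrolled | enrolled | 4 weeks, first three Dose C children only | No |

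Section 10.7 lists six time points per child. In Cohort 1 its spacing is meant to secure them for children 1 and 2 (2 × 6 = 12 of 3 × 6 = 18). The third child's six are tied to no dosing step.

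**2. Dose ratio.** 1.2 × 10^14 / 6.0 × 10^13 = 2.0.

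**3. Earliest timing.** Dosing is Day 1 and there is no Day 0 (SAP 1.1), so Day 30 falls 29 days after dosing. With doses at the minimum spacing, on calendar days 0, 28 and 56:

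- Dosed trigger, meeting on calendar day 56: the children are at study days 57, 29 and 1.
- Day 30 required: earliest review on calendar day 56 + 29 = 85, with the children at study days 86, 58 and 30.

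**4. How often a meeting would precede Day 30.** Assumptions, not in the documents: quarterly meetings are 91 days apart and the third dosing date is uniform between meetings.

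- Dosed trigger: 29/91 = 0.319, about 32%.
- Over a ±2-day visit window: 27/91 = 0.297 to 31/91 = 0.341.
- Meetings 98 or 84 days apart: 29/98 = 0.296 to 29/84 = 0.345.
- Literal enrolled trigger, with consent *s* days before dosing and the consent date uniform between meetings: (29 + *s*)/91. Screening runs from Day -60 to Day -2, so the range is 31/91 = 0.34 (*s* = 2) to 89/91 = 0.98 (*s* = 60).

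**5. From meeting to exposure.** These shares describe the meeting date, not a child's exposure. If the next child is dosed *L* days after the meeting, the dosed-trigger share with that dosing before the third child's Day 30 is max(0, 29 − *L*)/91. That gives 0.319, 0.165 and 0 at *L* = 0, 14 and 29. The documents do not give *L*.

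**6. Information lost with two children instead of three past Day 30.** The chance of having seen at least one event is 1 − (1 − p)^n (p assumed):

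| p | n = 2 | n = 3 |
|---|---|---|
| 0.10 | 19% | 27% |
| 0.20 | 36% | 49% |
| 0.30 | 51% | 66% |
| 0.50 | 75% | 88% |

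This treats the third child as contributing nothing before Day 30, so it is the worst case.

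**The case against.** The other side has a good deal to say, and most of it narrows the point.

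- **Serious events are already covered.** Protocol 12.1.1, 12.1.2 and 13.1.1 say enrolment will be interrupted or halted for unanticipated related Grade III or higher toxicity (12.1.2 adds symptoms requiring treatment; 7.5 is softer and says it may be). Section 10.7 has the sponsor confer with the DSMB on all related Grade III or higher events before enrolment continues. These rules apply to the third child whatever the meeting date. This stands, and it leaves mainly lower-grade findings exposed.
- **The charter may hold the rule.** Protocol 15 assigns the timing of scheduled reviews to the DSMB charter, which was not supplied. This stands: the point is about the protocol and SAP only.
- **Escalation is not automatic.** A reader might take 15.1 to mean that escalation follows by default. But 14.7.1.2 treats proceeding as the DSMB's judgement that Dose A is acceptably safe, Figure 1 requires the DSMB to find it acceptable, and section 15 lets the DSMB recommend suspension or modification. It could ask to wait.
- **The next-patient wording in 10.7.** One could read it as including the first Cohort 2 child. The sentence is limited to intervals within Cohort 1, so this does not close the gap. If it was intended, the fix merely says so.
- **The T-cell response.** Protocol 9.2.1 expects it at 2-4 weeks, which might suggest a toxicity window. The consequence named there is loss of transduced cells and transgene expression, so the case for Day 30 rests on the protocol's own within-cohort standard.

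Two stronger inferences are unsupported. First, the SAP's *may* for review 3 might look like a weakening of the protocol, but protocol 15.1 uses the same wording, which suits an optional cohort. Second, four treated Cohort 3 children might suggest that the fourth was dosed without adequate review. The documents do not show that any review lacked data.

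**Conclusion.** The concern holds in a limited form. Neither the protocol nor the SAP requires the third child's Day 30 data before the first Dose B child is treated or before Cohort 3 is expanded, and the trigger word differs for reviews 1 and 2. Dosed was probably intended.

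The exposed information is mainly lower-grade findings in one of three children. About 32% of meetings under a dosed trigger would come before that child's Day 30 (roughly 30% to 35% over the ranges shown). That rests on assumed 91-day meetings and a uniform third-dosing date. It is not an upper bound under the literal enrolled trigger. The charter may already close the gap.

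This is a worthwhile, cheap correction to a safety rule. It is not evidence of a lapse in conduct.

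**What to change.** 1. **Protocol 15.1 and SAP 13, all three reviews:** state that the review takes place after three patients in the cohort have been dosed and the third patient's safety data through Day 30 are available. Add that no patient receives Dose B before review 1, and that the cohort is not expanded before review 2 or 3.
2. **Protocol 14.7.1.2:** tie the recommendation to the first DSMB/DMC meeting, quarterly or ad hoc, after the Day 30 visit of the third patient dosed.
3. **Align** the synopsis, protocol 7.1 and 10.7, and SAP 3.5.

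**Cost, relative to a dosed trigger and under the same assumptions.** With an ad hoc meeting, the delay is at most 29 days and averages 29²/(2 × 91) = 4.6, about 5 days. With quarterly meetings only, about one review in three (29/91) waits a further 91 days, which averages 0.319 × 91 = 29 days over all reviews.

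Because the study has been terminated, these edits correct the text and inform any later study. They cannot change dosing here.
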